3.2 Additional Variables of Interest

Variable	Description	Variables and Source	Specifications
Randomization assignment	hearing aid assignment	assign	Binary 1: unilateral 2: bilateral
Clinical site	Which site - Duke or Vanderbilt?	which_site Character version: which_site_ch	Binary 1: Vanderbilt 2: Duke
Switch configuration at 6 months	Patients are given the opportunity to switch configuration at 3 months and make a final configuration	ha_switch_assign_6m	Binary: 1: Switched configuration 0: Didn't switch Switched configuration is defined as unilateral to bilateral or vice versa (do not count)

	choice at 6 months		switching unilateral to a different ear as a switch) Switched configuration also includes switching from 1 or 2 to 0
6-month final choice configuration	Patients are given to opportunity to make a final choice of hearing aid configuration at 6 months	ha_final_choice_6m Character version: ha_final_choice_6m_ch	Categorical: 
• Right• Left• Both• None• Missing

4 Statistical Analysis Plan

Deadline: To be completed by January 24, 2025.

4.1 Aim: compare all outcomes between the two assigned treatment arms

Compare the outcomes between the two assigned treatment arms (bilateral hearing aid and unilateral hearing aid) at 6 months.

Analysis: This will be reported for patients who have 6-month scores (“completers”). The analysis will be performed using either t-tests or Kruskal Wallis tests depending on whether or not the outcome distributions appear to be normally distributed for continuous outcomes. The total score for each survey at 6 months or the benefit score will be used as the outcomes. The Chi-Square test will be used for the APHAB Responder outcomes, with patient counts and relative frequencies reported.

The null hypothesis is that the means of the outcomes for the two treatment groups are the same.

$$H_0: \mu_{unilateral} = \mu_{bilateral}$$

Table 1: Distributions of 6-Month Outcomes or Benefit Scores by Assigned Treatment Group

	Unilateral (N=XXX)	Bilateral (N=XXX)	P-Value*
APHAB Global Change Score			XXX
N	XXX	XXX	
Missing	XXX	XXX	
Mean (SD)	XXX (XXX)	XXX (XXX)	
Median	XXX	XXX	
Q1, Q3	XXX, XXX	XXX, XXX	
Range	XXX - XXX	XXX - XXX	
APHAB Responder (25 Units)**			XXX
No	XXX (%)	XXX (%)	
Yes	XXX (%)	XXX (%)	
Ineligible to Drop 25 Units	XXX	XXX	
APHAB Responder (15 Units)**			XXX
No	XXX (%)	XXX (%)	
Yes	XXX (%)	XXX (%)	

Ineligible to Drop 15 Units	XXX	XXX	
SADL Global Score			XXX
N	XXX	XXX	
Missing	XXX	XXX	
Mean (SD)	XXX (XXX)	XXX (XXX)	
Median	XXX	XXX	
Q1, Q3	XXX, XXX	XXX, XXX	
Range	XXX - XXX	XXX - XXX	
HHI-E Change Score			XXX
N	XXX	XXX	
Missing	XXX	XXX	
Mean (SD)	XXX (XXX)	XXX (XXX)	
Median	XXX	XXX	
Q1, Q3	XXX, XXX	XXX, XXX	
Range	XXX - XXX	XXX - XXX	
IOI-HA Total Score			XXX
N	XXX	XXX	
Missing	XXX	XXX	
Mean (SD)	XXX (XXX)	XXX (XXX)	
Median	XXX	XXX	
Q1, Q3	XXX, XXX	XXX, XXX	
Range	XXX - XXX	XXX - XXX	
SSQ Change Score			XXX
N	XXX	XXX	
Missing	XXX	XXX	
Mean (SD)	XXX (XXX)	XXX (XXX)	
Median	XXX	XXX	
Q1, Q3	XXX, XXX	XXX, XXX	
Range	XXX - XXX	XXX - XXX	

*T-test/Kruskal Wallis or Chi-Square test

**Denominator for percentages does not include patients ineligible to drop 'x' units

We will also describe the distributions of additional variables at 6-month visit as appropriate by assigned treatment (subscales and total scores where change score was reported above). We will also create boxplots for APHAB Global total score and change score by randomization. These figures may supplement Table 1 above.

Table 2: Distributions of Clinical Variables by Assigned Treatment

	Unilateral (N=XXX)	Bilateral (N=XXX)
APHAB Global Total Score (6 Months)		
N	XXX	XXX
Missing	XXX	XXX
Mean (SD)	XXX (XXX)	XXX (XXX)
Median	XXX	XXX
Q1, Q3	XXX, XXX	XXX, XXX
Range	XXX - XXX	XXX - XXX
APHAB EC Subscale (6 Months)		
N	XXX	XXX
Missing	XXX	XXX

Mean (SD)	XXX (XXX)	XXX (XXX)
Median	XXX	XXX
Q1, Q3	XXX, XXX	XXX, XXX
Range	XXX - XXX	XXX - XXX
APHAB EC Subscale Change Score		
N	XXX	XXX
Missing	XXX	XXX
Mean (SD)	XXX (XXX)	XXX (XXX)
Median	XXX	XXX
Q1, Q3	XXX, XXX	XXX, XXX
Range	XXX - XXX	XXX - XXX
APHAB BN Subscale (6 Months)		
N	XXX	XXX
Missing	XXX	XXX
Mean (SD)	XXX (XXX)	XXX (XXX)
Median	XXX	XXX
Q1, Q3	XXX, XXX	XXX, XXX
Range	XXX - XXX	XXX - XXX
APHAB BN Subscale Change Score		
N	XXX	XXX
Missing	XXX	XXX
Mean (SD)	XXX (XXX)	XXX (XXX)
Median	XXX	XXX
Q1, Q3	XXX, XXX	XXX, XXX
Range	XXX - XXX	XXX - XXX
APHAB RV Subscale (6 Months)		
N	XXX	XXX
Missing	XXX	XXX
Mean (SD)	XXX (XXX)	XXX (XXX)
Median	XXX	XXX
Q1, Q3	XXX, XXX	XXX, XXX
Range	XXX - XXX	XXX - XXX
APHAB RV Subscale Change Score		
N	XXX	XXX
Missing	XXX	XXX
Mean (SD)	XXX (XXX)	XXX (XXX)
Median	XXX	XXX
Q1, Q3	XXX, XXX	XXX, XXX
Range	XXX - XXX	XXX - XXX
APHAB AV Subscale (6 Months)		
N	XXX	XXX
Missing	XXX	XXX
Mean (SD)	XXX (XXX)	XXX (XXX)
Median	XXX	XXX
Q1, Q3	XXX, XXX	XXX, XXX
Range	XXX - XXX	XXX - XXX
APHAB AV Subscale Change Score		
N	XXX	XXX
Missing	XXX	XXX
Mean (SD)	XXX (XXX)	XXX (XXX)

Median	XXX	XXX
Q1, Q3	XXX, XXX	XXX, XXX
Range	XXX - XXX	XXX - XXX
SADL Positive Effect Subscale (6 Months)		
N	XXX	XXX
Missing	XXX	XXX
Mean (SD)	XXX (XXX)	XXX (XXX)
Median	XXX	XXX
Q1, Q3	XXX, XXX	XXX, XXX
Range	XXX - XXX	XXX - XXX
SADL Service Cost Subscale (6 Months)		
N	XXX	XXX
Missing	XXX	XXX
Mean (SD)	XXX (XXX)	XXX (XXX)
Median	XXX	XXX
Q1, Q3	XXX, XXX	XXX, XXX
Range	XXX - XXX	XXX - XXX
SADL Negative Features Subscale (6 Months)		
N	XXX	XXX
Missing	XXX	XXX
Mean (SD)	XXX (XXX)	XXX (XXX)
Median	XXX	XXX
Q1, Q3	XXX, XXX	XXX, XXX
Range	XXX - XXX	XXX - XXX
SADL Personal Image Subscale (6 Months)		
N	XXX	XXX
Missing	XXX	XXX
Mean (SD)	XXX (XXX)	XXX (XXX)
Median	XXX	XXX
Q1, Q3	XXX, XXX	XXX, XXX
Range	XXX - XXX	XXX - XXX
HHI-E Total Score (6-Month)		
N	XXX	XXX
Missing	XXX	XXX
Mean (SD)	XXX (XXX)	XXX (XXX)
Median	XXX	XXX
Q1, Q3	XXX, XXX	XXX, XXX
Range	XXX - XXX	XXX - XXX
HHI-E Social/Situational Subscale (6-Month)		
N	XXX	XXX
Missing	XXX	XXX
Mean (SD)	XXX (XXX)	XXX (XXX)
Median	XXX	XXX
Q1, Q3	XXX, XXX	XXX, XXX
Range	XXX - XXX	XXX - XXX

HHI-E Emotional Subscale (6-Month)

N	XXX	XXX
Missing	XXX	XXX
Mean (SD)	XXX (XXX)	XXX (XXX)
Median	XXX	XXX
Q1, Q3	XXX, XXX	XXX, XXX
Range	XXX - XXX	XXX - XXX

SSQ Overall Score (6-Month)

N	XXX	XXX
Missing	XXX	XXX
Mean (SD)	XXX (XXX)	XXX (XXX)
Median	XXX	XXX
Q1, Q3	XXX, XXX	XXX, XXX
Range	XXX - XXX	XXX - XXX

SSQ Speech/Hearing Subscale (6-Month)

N	XXX	XXX
Missing	XXX	XXX
Mean (SD)	XXX (XXX)	XXX (XXX)
Median	XXX	XXX
Q1, Q3	XXX, XXX	XXX, XXX
Range	XXX - XXX	XXX - XXX

SSQ Spatial/Hearing Subscale (6-Month)

N	XXX	XXX
Missing	XXX	XXX
Mean (SD)	XXX (XXX)	XXX (XXX)
Median	XXX	XXX
Q1, Q3	XXX, XXX	XXX, XXX
Range	XXX - XXX	XXX - XXX

SSQ Qualities of Hearing Subscale**(6-Month)**

N	XXX	XXX
Missing	XXX	XXX
Mean (SD)	XXX (XXX)	XXX (XXX)
Median	XXX	XXX
Q1, Q3	XXX, XXX	XXX, XXX
Range	XXX - XXX	XXX - XXX

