4.2 Describe APHAB Global Score Distributions and Responder Status

We will describe the distribution of APHAB global score at baseline (unaided) and 3 months (aided), along with the change score and responder status (both definitions) by hearing aid assignment in Table 2.

Table 2: APHAB Global Score Distributions and Responder Status

	Unilateral (N=XXX)	Bilateral (N=XXX)	Total (N=XXX)
APHAB Global Score (Baseline)			
N	XXX	XXX	XXX
Missing	XXX	XXX	XXX
Mean (SD)	XXX (XXX)	XXX (XXX)	XXX (XXX)
Median	XXX	XXX	XXX
Q1, Q3	XXX , XXX	XXX , XXX	XXX , XXX
Range	XXX - XXX	XXX - XXX	XXX - XXX
APHAB Global Score (3 Months)			
N	XXX	XXX	XXX
Missing	XXX	XXX	XXX
Mean (SD)	XXX (XXX)	XXX (XXX)	XXX (XXX)
Median	XXX	XXX	XXX
Q1, Q3	XXX , XXX	XXX , XXX	XXX , XXX
Range	XXX - XXX	XXX - XXX	XXX - XXX
APHAB Change Score			
N	XXX	XXX	XXX
Missing	XXX	XXX	XXX
Mean (SD)	XXX (XXX)	XXX (XXX)	XXX (XXX)
Median	XXX	XXX	XXX
Q1, Q3	XXX , XXX	XXX , XXX	XXX , XXX
Range	XXX - XXX	XXX - XXX	XXX - XXX
APHAB Responder (25 Units)*			
No	XXX (%)	XXX (%)	XXX (%)
Yes	XXX (%)	XXX (%)	XXX (%)
Ineligible to Drop 25 Units	XXX	XXX	XXX
APHAB Responder (15 Units)*			
No	XXX (%)	XXX (%)	XXX (%)
Yes	XXX (%)	XXX (%)	XXX (%)
Ineligible to Drop 15 Units	XXX	XXX	XXX

*Denominator for percentages does not include patients ineligible to drop 'X' units

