4.3 Primary aim: compare APHAB scores between the two arms

Compare the APHAB change scores between the two arms (bilateral hearing aid and unilateral hearing aid) at the end of month 3 vs baseline.

Analysis: This will be done for all randomized patients who have both baseline and 3 month scores (a “completers” analysis). The primary analysis will be performed by linear regression and include randomized assignment and clinical site as covariates.

$$APHAB \text{ change score} = \beta_0 + \beta_1 * \text{treatment} + \beta_2 * \text{site}$$

Table 3: Linear Regression Beta Estimates
Outcome Modelled: APHAB Change Score

Covariate	Beta	95% C.I.	P-Value*
Hearing Aid Assignment (Reference: Bilateral)			
Unilateral	XXX	(XXX , XXX)	XXX
Clinical Site (Reference: Duke)			
Vanderbilt	XXX	(XXX , XXX)	XXX

*Using XXX statistic

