4.6 Analyze APHAB binary response at 3 months

Patients with a decrease of at least 25 units on the APHAB scale at month 3 compared to baseline unaided APHAB will be defined as “responders.” Patients who do not meet this criterion of 25 units, do not return, or do not have a score at month 3 will be defined as “non-responders.” If there are any patients with unaided APHAB scores of less than 25, these patients will be excluded as they are not eligible to drop 25 units.

Analysis 1: This will be done for all randomized patients who are eligible, including those missing APHAB change scores. This analysis will be performed by logistic regression and include randomized assignment and clinical site as covariates.

$$\text{Binary APHAB change score} = \beta_0 + \beta_1 * \text{treatment} + \beta_2 * \text{site}$$

Table 6: Logistic Regression OR Estimates

Outcome Modelled: Binary APHAB Change Score Response (25 Unit)

Covariate	OR	95% C.I.	P-Value*
Hearing Aid Assignment (Reference: Bilateral)			
Unilateral	XXX	(XXX , XXX)	XXX
Clinical Site (Reference: Duke)			
Vanderbilt	XXX	(XXX , XXX)	XXX

*Using XXX statistic

Analysis 2 (heterogeneity of treatment effects): This analysis will be performed by logistic regression and include randomized assignment, clinical site, a given variable of interest (denoted by S), and interactions between treatment and the variable of interest, with separate models fit for each variable of interest. The two variables of interest that decided to investigate are income group (simplified version – below median, above median, prefer not to answer) and hearing loss classification (mild, moderate). Interactions will be tested at the 0.15 level. If the overall test for the interaction is significant, forest plots will be constructed to examine the heterogeneity of treatment effect and formal treatment by factor interaction terms tested in the models. The general model structure is:

$$\text{Binary APHAB change score} = \beta_0 + \beta_1 * \text{treatment} + \beta_2 * \text{site} + \beta_S * S + \beta_{ST} * S * \text{treatment}$$

We will report the joint test p-value for the interaction term. If significant, we will report odds ratios and 95% confidence intervals.

Table 7 Logistic Regression OR Estimates for Variable S Model
Outcome Modelled: Binary APHAB Change Score Response (25 Unit)

Covariate	OR	95% C.I.	P-Value*
Hearing Aid Assignment (Reference: Bilateral)	XXX	(XXX , XXX)	XXX
Unilateral	XXX	(XXX , XXX)	XXX

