2.3 Data Acquisition

Fill in all relevant information:

Study design	Randomized controlled trial with 2 arms (bilateral hearing aid, unilateral hearing aid) Note: Randomization was stratified by clinical site.
Data source/how the data were collected	Screening information pulled from EHR data Baseline surveys captured via in-person interview and recorded in REDCap
Contact information for team member responsible for data collection/acquisition	All data access is through [REDACTED] [REDACTED]. Questions on data validity will go to PI: [name] ([contact])
Date or version (if downloaded, provide date)	10.28.2024
Data transfer method and date	Direct data extraction from REDCap
Where dataset is stored	REDCap Extracted data and analytic datasets are stored on a secure drive in the CRU folder: \\duhs-vclin-nc1\dusom_biostats_fs\Data\BiostatsCore\CRU\Head and Neck\[name]\PCORI_Pro00106077\Data pulls

--	--

Notes: Additional variable details for all variables can be found in the “PCORI Variable Details” Excel file. Scoring details can be found in “PCORI Scoring 20240923”.

3 Outcomes, Exposures, and Additional Variables of Interest

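### The month-6 APHAB comparisons by assigned arm leave out site, the randomisation stratum, and report no effect estimate or confidence interval, unlike the month-3 analyses of the same outcomes (minor)

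*SAP*

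**What the plan says.** **Randomisation.** Section 2.3 of the 6-Month SAP records the stratum: "Randomization was stratified by clinical site". Section 3.2 lists site among the variables, but no analysis in that SAP uses it.

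**Month 3 (Primary SAP).** For APHAB change, section 4.3 says: "The primary analysis will be performed by linear regression and include randomized assignment and clinical site as covariates". For response at the 25-unit threshold, section 4.6 says: "This analysis will be performed by logistic regression and include randomized assignment and clinical site as covariates", and the same model is repeated at 15 units. Tables 3, 6 and 8 give a beta or odds ratio with a 95% interval. The responder population is explicit: "This will be done for all randomized patients who are eligible, including those missing APHAB change scores".

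**Month 6 (6-Month SAP, 4.1).** The analysis covers patients with a month-6 score. For continuous outcomes, "The analysis will be performed using either t-tests or Kruskal Wallis tests depending on whether or not the outcome" looks normally distributed. For response, "The Chi-Square test will be used for the APHAB Responder outcomes, with patient counts and relative frequencies reported". Table 1 shows summary statistics or counts, plus a p-value. The planned figures are boxplots.

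**Reasons given.** Section 4.4 of the 6-Month SAP explains why the repeated-measures models were dropped. It does not say why site was.

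**The concern.** The 6-Month SAP states a superiority hypothesis for bilateral aids (1.1) and has dropped the longitudinal model (4.4). Section 4.1 is therefore the only formal comparison of month-6 APHAB by assigned arm. Two things are at stake.

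- **Test behaviour.** Stratified randomisation balances the arms within site. A test that ignores site still charges between-site variation to error. If sites differ, it rejects less often than its nominal level and loses power.
- **Reported result.** A p-value shows neither the size nor the precision of the arm effect. A non-significant month-6 chi-square could be read as no difference when the data are compatible with a sizeable one. The reader would also have a site-adjusted odds ratio with an interval at month 3 and nothing of that kind at month 6.

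**Working it through.** The plan states no figure to reproduce here. The documents give no site effect and no site sizes, so the calculations show a range.

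**Inputs from the documents.** Planned enrolment 350 (Protocol section 6), allocation 1:1 (Protocol section 4), APHAB SD 25 (Primary SAP 3.1). **Assumed.** Two equal sites, full data, the site gaps shown, and a true odds ratio of 0.6 for the power figures.

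**1. APHAB change.** With site difference D and total SD 25, site explains R² = 0.25 × D² / 625. The standard error without site exceeds that with site by the factor 1/√(1 − R²). The unadjusted 95% half-width is 1.96 × 25 × √(4/350) = 5.24 units.

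| D (units) | R² | SE ratio | Half-width with site |
|---|---|---|---|
| 0 | 0 | 1.000 | 5.24 |
| 5 | 0.010 | 1.005 | 5.21 |
| 10 | 0.040 | 1.021 | 5.13 |
| 12.5 | 0.0625 | 1.033 | 5.07 |

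Even a site difference of half an SD costs only about 3% of the standard error.

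**2. APHAB response.** Simulation of 40,000 trials with 348 patients (174 per arm, 87 per arm per site). Pearson chi-square is compared with the Cochran-Mantel-Haenszel (CMH) test stratified by site, which stands in for the site-adjusted logistic test. Site rates are those of the bilateral arm.

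| Site rates | Type I error, chi-square / CMH | Power at OR 0.6, chi-square / CMH |
|---|---|---|
| 50/50 | 4.7% / 4.7% | 64.3% / 64.3% |
| 45/55 | 4.8% / 4.8% | 64.0% / 64.7% |
| 40/60 | 4.3% / 5.1% | 61.1% / 64.1% |
| 35/65 | 3.8% / 5.1% | 56.4% / 61.0% |
| 30/70 | 3.0% / 5.1% | 49.6% / 58.0% |

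A large-sample check for 40/60: the pooled variance over the within-site variance is 0.25/0.24 = 1.042, with square root 1.021. Type I error is then 2[1 − Φ(1.96 × 1.021)] ≈ 4.5%. The simulated 4.3% is a little lower. The 4.7% with no site gap suggests that the discreteness of counts contributes.

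**3. What the missing interval hides.** At an assumed 40% response in both arms, the 95% half-width of the risk difference is 1.96 × √(2 × 0.24/n). This is 10.3 percentage points at n = 175 per arm and 11.5 at n = 140.

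**4. What can be recovered.** Illustrative counts of 70/175 and 90/175 give a crude odds ratio of (70 × 85)/(105 × 90) = 0.63. The standard error of its logarithm is √(1/70 + 1/105 + 1/90 + 1/85) = 0.216, so the 95% interval is 0.41 to 0.96. A crude odds ratio does not estimate quite the same quantity as the month-3 one. A within-site odds ratio of 0.60 corresponds to a crude value of 0.61 at site rates 40/60 and 0.65 at 30/70.

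**5. Population.** Primary SAP 4.6 keeps eligible patients without a score as non-responders. Section 3.1 of the 6-Month SAP defines response in the same way, but its section 4.1 restricts the analysis to patients with a month-6 score. Under 4.1 the rule for missing scores would have nobody to act on.

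**The case against.** Several arguments on the other side have force.

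- **The tests are valid.** An unadjusted test after stratified randomisation errs on the conservative side. The loss depends on a site effect that the documents do not give, and it is small for moderate gaps. This stands, and it is why the point is minor.
- **Month 6 is secondary.** The protocol describes this follow-up as exploratory, and the 3-Month Secondary SAP (4.1) also tests its outcomes without site. This stands for the SADL, HHI-E, IOI-HA and SSQ. Adding site for those four at month 6 alone would create a mismatch with month 3. It does not explain APHAB, which has site in its month-3 models. Nor is site dropped from all data after month 3: the EMA SAP (4.2) keeps it for both periods.
- **Crude comparison is possible.** A reader might infer that the two visits cannot be compared at all. The documents do not support that. Section 4.2 of the Primary SAP tabulates month-3 results "along with the change score and responder status (both definitions) by hearing aid assignment in Table 2", in much the same layout as month-6 Table 1, so crude effects with intervals can be worked out at both visits.
- **Intervals are not inflated.** A reader might also infer that the month-6 intervals will be too wide. None is planned. For the odds ratio the direction reverses: adjusting for site increases the standard error of the log odds ratio, by 2.1% at site rates 40/60 with odds ratio 0.6. The adjusted test still has more power, because the within-site log odds ratio lies further from zero.
- **Switching.** Participants may change configuration at month 3. A site term does not make a month-6 contrast by assigned arm a measure of sustained use of the assigned configuration.

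**Conclusion.** The point holds as a minor one. In the month-6 APHAB comparisons by assigned arm, the randomisation stratum is left out without a stated reason, and no effect estimate or interval is planned. Both differ from the month-3 analyses of the same outcomes.

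The statistical cost is small and conditional. For assumed site gaps of 10 to 20 points in response, chi-square type I error is about 4.8% to 4.3%, and the power loss is about 1 to 3 points. It reaches about 8 points only at a 40-point gap. For APHAB change the standard error is at most about 3% larger for site differences up to half an SD. These figures assume equal sites, about 350 patients and SD 25. With no site effect the loss is zero.

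The missing estimate does not depend on those assumptions. What the planned output lacks is a like-for-like site-adjusted effect at the two visits. The conflict over the responder population is a further obstacle that a site term alone would not remove.

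**What to change.** In section 4.1 of the 6-Month SAP, for the APHAB outcomes only:

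1. Analyse month-6 APHAB change with the linear model of Primary SAP 4.3 (assignment and site). Report the arm difference with its 95% interval.
2. Analyse both responder definitions with the logistic model of Primary SAP 4.6 (assignment and site). Report the odds ratio with its 95% interval.
3. Keep the t-test or Kruskal-Wallis test and the chi-square as supportive, if wanted.
4. Reconcile 3.1 with 4.1 by stating one responder population that matches month 3: all eligible randomised patients, with a missing score counted as non-response.
5. Show the month-3 and month-6 APHAB arm effects side by side.

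Adding site for the other month-6 outcomes is optional, since their month-3 tests omit it too.

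The cost is SAP wording and reuse of month-3 code, with no new data. The 6-Month SAP gives a data date of 10.28.2024, so the change should be logged as a dated amendment. If the planned tests have already been run, the amendment should say so.

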4.2 Aim: Compare 6-month outcomes by 6-month final choice of HA configuration

Compare the outcomes between the two HA configuration choice groups (bilateral hearing aid and unilateral hearing aid) at 6 months.

Analysis: Similar analysis and table as in Aim 1, Table 1, but with columns defined by 6-month HA configuration choice [Table 3].

4.3 Aim: Compare 6-month outcomes by 6-month configuration switching status relative to baseline

Compare the outcomes between the two groups (switched or did not switch from assigned HA configuration) at 6 months.

Analysis: Similar analysis and table as in Aim 1, Table 1, but with columns defined by 6-month HA switching status relative to baseline [Table 4].

4.4 Initially planned analyses that we will not do

We had initially planned to estimate repeated measures mixed models for all outcomes gathered at baseline, 3-months, and 6-months with randomized treatment assignment as the covariate of interest. However, given the propensity for participants to switch hearing aid configurations at 3-months and that there are only 2 follow-up timepoints, we deemed it more appropriate to look at the outcomes cross-sectionally rather than longitudinally.

5 Future Plans

There are additional items we may wish to explore in the future, at which point a new SAP will be developed. Ideas include looking at:

- Additional Glasgow Hearing Aid Benefit Profile measures
- Mask questions
- Additional hearing aid hours of use
- Unscheduled visits

Statistical Analysis Plan (SAP) – EMAs

Project: Evaluation of Unilateral vs Bilateral Hearing Aids for the Treatment of Age-related Hearing Loss

IRB Number: Pro00106077

Investigator(s): [name], AuD, PhD

Biostatisticians: [REDACTED]

Original Creation Date: 02.18.2022

Version Date: 12.02.2024

Investigator Agreement

- All statistical analyses included in an abstract or manuscript should reflect the work of the biostatistician(s) listed on this SAP. No changes or additional analyses should be made to the results or findings without discussing with the project biostatistician(s).
- All biostatisticians on this SAP should be given sufficient time to review the full presentation, abstract, manuscript, or grant and be included as co-authors on any abstract or manuscript resulting from the analyses.
- If substantial additional analysis is necessary or the aims of the project change, a new SAP will need to be developed.
- Publications resulting from this SAP are supported in part by the Duke CTSA and must cite grant number UL1TR002553 and be submitted to PubMed Central.
- I have reviewed the SAP and understand that any changes must be documented.

Acknowledged by: Click or tap here to enter text.

Date: Click or tap to enter a date.

Activity Log

02.18.2022 Created SAP for GHABP and EMA outcomes
02.21.2022 Added details to analysis
03.14.2022 Updated based on discussion
01.26.2023 Add additional details to variables and updates reflective of changes made in other SAPs
05.31.2024 Moved 6-month data to Future Plans section
12.02.2024 Removed GHABP and moved user-nominated scenarios to Future Plans section

Acronyms

APHAB	Abbreviated Profile of Hearing Aid Benefit
EMA	Ecological Momentary Assessment
GHABP	Glasgow Hearing Aid Benefit Profile
IOI-HA	International Outcomes Inventory for Hearing Aids
SADL	Satisfaction with Amplification in Daily Life
SSQ	Speech Spatial Qualities
HHIE	Hearing Handicap Inventory for Elderly

1 Study Overview

Background/Introduction: The overall goal of the project is to determine the benefit of unilateral or bilateral hearing aid fittings in adults with mild-to-moderate age-related hearing loss. This will address the lack of high-quality evidence supporting bilateral hearing aids over unilateral hearing aids. This project will use a randomized controlled trial with two treatment arms: a bilateral hearing aid fitting group and a unilateral hearing aid fitting group.

